3.1 General Study Design and Plan

Approximately 100 patients with moderate to severe atopic dermatitis will be included in this multicenter, double-blind, placebo controlled, phase IIa study. All subjects will sign an informed consent and undergo screening for study eligibility. Subjects will be randomized (1:1) at baseline visit to either receive oral DS107G 2 g, or placebo once daily for 8 weeks in a fasting state.

Subjects will come to the clinic on 6 occasions: at screening, baseline, week 2, week 4, week 8 (end of treatment/early termination) and week 10 (follow-up). All subjects will exit the study at the Week 10 visit. The primary efficacy variable will be the proportion of patients achieving an IGA of 0 (clear) or 1 (almost clear) and a decrease of at least 2 points in IGA at week 8. Secondary efficacy variables will include IGA at other visits, pruritus (obtained from the SCORAD visual analog scale), EASI, BSA, POEM, DLQI, SCORAD and TEWL (for selected sites only). Safety will be assessed through adverse events, physical examination, vital signs and safety laboratory tests (including pregnancy tests for women of childbearing potential). Pharmacokinetic samples will be obtained at Baseline (Day 0), week 4 and week 8 visits in order to measure total and free DGLA plasma trough levels. A separate plasma sample will be retained for later analysis of total fatty acid profile and interleukin profile.

The study flow chart of all assessment and timing is presented in Figure 1.

Figure 1. Study Flow Chart

Visit	Screening	Baseline	Week 2	Week 4	Week 8 / ET visit	Follow up visit / Week 10
Day	-30 to -1	0	14 (± 2)	28 (± 2)	56 (± 2)	70 (±3)
Informed Consent	X					
Demographics	X					
Medical / Surgical History	X	X				
Ongoing medical history ^Y					X	X
Review Inclusion/Exclusion Criteria	X	X				
Hanifin and Rajka criteria	X					
Assign subject identifier number	X					
Randomization		X				
Concomitant Medications	X	X	X	X	X	X ^δ
Safety labs and inflammation biomarkers: Serum Chemistry (including FSH levels at screening when applicable ^Y and interleukin profile), Coagulation, Hematology, urinalysis	X ^Φ	X		X	X	(X**) ^{Φ, δ}
Pharmacokinetics (pre-dose blood draw) ^{††}		X		X	X	
Blood draw for fatty acid profile sample ^{††}		X		X	X	
Pregnancy Test (β-hCG if female of childbearing potential)*	X	X	X	X	X	X ^δ
Vital Signs	X	X	X	X	X	X ^δ
Physical Examination	X			X	X	X ^δ
BMI	X	X			X	
Study Drug Administration (on site) [€]		X		X		§
Dispense Study Drug		X	X	X		
Collect Study Drug			X	X	X	
Dispense Subject Compliance Log		X	X	X		
Collect and Review Subject Compliance Log			X	X	X	
Capsule count			X	X	X	
BSA	X	X	X	X	X	X
IGA	X	X	X	X	X	X
EASI assessment		X	X	X	X	X
SCORAD assessment / VAS pruritus assessment		X	X	X	X	X
POEM questionnaire		X	X	X	X	X
DLQI questionnaire		X	X	X	X	X
TEWL (selected sites only)		X	X	X	X	X
Adverse Events [†]	X [†]	X	X	X	X	X ^δ

^Y: For women greater than 40 and less than 60 years of age who have had a cessation of menses for at least 12 months but less than 24 months

^{**}: Only if clinically significant change from baseline in safety lab results at week 8

*: Serum pregnancy test at screening and week 8 / ET visits, urine test pregnancy for all other visits
††: If a subject took study medication prior to the visit, he/she will be required to come back the following day for PK blood draws.
€: Subjects must be fasting for at least 8 hours before and 60 minutes after drug administration
§: Subjects will be instructed to take their last study drug dose the day preceding week 8 visit.
†: Collection of AE will start after the first study drug administration
¥: Assessment if any ongoing condition has improved since baseline.
Φ: Interleukin profile will not be evaluated at screening and week 10.
δ: In the case the subject ends the study before completion, the subject will also return 2 weeks after the ET visit for safety assessment listed at Week 10.

3.2 Inclusion-Exclusion Criteria and General Study Population

To participate in the study, subjects must meet all the inclusion criteria and none of the exclusion criteria.

3.2.1 Inclusion Criteria

Subjects must meet all of the following criteria to be eligible for this study:

- Male or female subject aged 18 years and older on the day of signing the informed consent form (ICF).
- Clinically confirmed diagnosis of active atopic dermatitis according to Hanifin and Rajka criteria.
- Moderate to severe atopic dermatitis at baseline as defined by an IGA of minimum 3 at baseline visit.
- Atopic dermatitis covering minimum 10% of the body surface area at baseline.
- Body mass index (BMI) is between 18 and 35 kg/m² inclusively.
- Female patients of childbearing potential must use adequate contraception or have a sterilized partner for the duration of the study: systemic hormonal contraceptives, intrauterine device or barrier method of contraception in conjunction with spermicide, or agree to sexual abstinence. Hormonal contraceptives must be on a stable dose for at least one month before baseline. Note: Women of non-child bearing potential are:
 - women who have had surgical sterilization (hysterectomy or bilateral oophorectomy or tubal ligation)
 - women greater than 60 years of age
 - women greater than 40 and less than 60 years of age who have had a cessation of menses for at least 12 months and a follicle-stimulating hormone (FSH) test confirming non-childbearing potential (FSH \geq 40 mIU/mL) or cessation of menses for at least 24 months without FSH levels confirmed.
- Patients who are able and willing to stop treatment for atopic dermatitis throughout the study (except for allowed emollients).
- Capable and willing to give signed informed consent and the consent must be obtained prior to any study related procedures.

3.2.2 Exclusion Criteria

Subjects must not have the following to be eligible for this study:

- Female patients with positive pregnancy test at screening or Day 0 visit (baseline) or lactating women.
- Any clinically significant controlled or uncontrolled medical condition or laboratory abnormality that would, in the opinion of the investigator, put the patient at undue risk or interfere with interpretation of study results.
- Clinically significant impairment of renal or hepatic function.
- Other skin conditions that might interfere with atopic dermatitis diagnosis and/or evaluation (such as psoriasis or current viral, bacterial and fungal skin infections).
- History of hypersensitivity to any substance in DS107G or placebo capsules.
- Use of biologics 3 months prior to start of treatment/ Day 0 visit (baseline), or 5 half-lives (whichever is longer).
- Use of systemic treatments (other than biologics) that could affect atopic dermatitis less than 4 weeks prior to baseline visit (Day 0), e.g. retinoids, calcineurin inhibitors, methotrexate, cyclosporine, hydroxycarbamide (hydroxyurea), azathioprine and oral/injectable corticosteroids; Intranasal corticosteroids and inhaled corticosteroids for stable medical conditions are allowed.
- Treatment with any experimental drug within 30 days prior to Day 0 visit (baseline), or 5 half lives (whichever is longer).
- Excessive sun exposure, use of tanning booths or other ultraviolet (UV) light sources 4 weeks prior to Day 0 visit (baseline) and/or is planning a trip to sunny climate to use tanning booths or other UV sources between screening and follow-up visits.
- Use of any topical medicated treatment for atopic dermatitis 2 weeks prior to start of treatment/Day 0 visit (baseline), including but not limited to, topical corticosteroids, calcineurin inhibitors, tars, bleach, antimicrobials and bleach baths.
- Use of topical products containing urea, ceramides or hyaluronic acid for 2 weeks prior to Day 0.
- Use of anti-histamines for atopic dermatitis within 2 weeks of baseline.
- Significant uncontrolled cardiovascular (a history of ECG abnormalities that are clinically significant in the opinion of the investigator), neurologic, malignant, psychiatric, respiratory or hypertensive disease, as well as diabetes and arthritis.
- Medical history of chronic infectious disease (e.g., hepatitis B, hepatitis C or infection with human immunodeficiency virus).
- History of clinically significant drug or alcohol abuse in the last year prior to Day 0 (baseline).

3.4 Study Variables

3.4.1 Demographics and Baseline Characteristics

Age calculated in years is defined as the difference between the informed consent date and the birthdate.

Gender is a code list where 1 equals Male and 2 equals Female.

Height in centimeters measured to the nearest centimeter.

Weight in kilograms (kg) measured to one decimal place.

Body Mass Index (BMI) will be calculated as the weight (kg) divided by the square of height (m) and rounded to one decimal place (kg/m²).

Race is an integer ranging from 1 to 6, where 1 corresponds to American Indian or Alaska Native, 2 corresponds to Asian, 3 corresponds to Black or African American, 4 corresponds to Native Hawaiian or Other Pacific Islander, 5 corresponds to White, and 6 corresponds to Other.

Ethnicity is code list where 1 corresponds to 'Hispanic or Latino' and 2 corresponds to 'Not Hispanic or Latino'.

Medical History

Medical history will be coded using the Body System Code as the following: Eyes-Ears-Nose-Throat, Respiratory (Asthma/Other), Cardiovascular, Gastrointestinal, Hepatobiliary, Genitourinary/ Renal, Reproductive, Neurological, Endocrine, Hematological, Musculoskeletal, Dermatologic, Extremities, Immunological, Psychiatric, and Allergies.

Medications

Medications will be coded using the Preferred Term from the WHO Drug Dictionary (Sept-2014 B2). If the start and end dates of the medication are prior to the study drug start date then the medication will be coded as prior medication. Otherwise the medication will be considered as concomitant medications.

3.4.2 Efficacy Variables

3.4.2.1 Primary Efficacy Variable

The primary efficacy variable is the **Investigator's Global Assessment (IGA)** of Disease Severity and will be assessed at each visit. The IGA is a global assessment of the current state of the disease. It is a 6-point morphological assessment of overall disease severity and will be determined according to the following definitions:

Score	Grade	Definition
0	Clear	No evidence of disease with the exception of residual pigment changes and/or xerosis
1	Almost clear	Perceptible erythema, papulation/infiltration
2	Mild	Mild erythema, papulation/infiltration
3	Moderate	Moderate erythema, papulation/infiltration
4	Severe	Severe erythema, papulation/infiltration
5	Very Severe	Severe erythema, papulation/infiltration with oozing/crusting

Change from Baseline will be calculated as the value at the visit minus the value at Baseline. The change will be calculated at Week 2, Week 4, Week 8, and Week 10. Percent change from baseline will also be calculated. In addition, change and percent change from Week 8 to Week 10 will be calculated.

The IGA will be also examined using the following criteria:

- IGA of 0 (clear) or 1 (almost clear) at Week 8;
- at least a 2-point decrease in IGA at Week 8;
- at least a 1-point decrease in IGA at Week 8;
- No Change or Increased from Baseline in IGA at Week 8

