5.3 Missing Data/Multiple Observations

No imputation will be done for all population and all parameters, except for the primary endpoint. A supportive analysis using the last observation carried forward (LOCF) method will be performed on responder analysis (see section 7.1 for details).

In the event that two values were collected for the same visit, the scheduled assessment value will be retained in the analyses, unless otherwise specified (e.g. lab error). However, all values will be presented in the data listings. Laboratory values of '< X' or '> X' will be set to 'X' for the analysis.

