7.2 Secondary Efficacy Analyses

The second efficacy endpoints are:

- Change from baseline in IGA at week 2, 4, and 8
- Change from baseline in EASI at week 2, 4, and 8
- Change from baseline in POEM at week 2, 4, and 8
- Change from baseline in DLQI at week 2, 4, and 8
- Change from baseline in SCORAD at week 2, 4, and 8
- Change from baseline in VAS at week 2, 4, and 8
- Change from baseline in BSA at week 2, 4, and 8
- Proportion of patients achieving at least 1-point decrease in IGA at Week 8

All secondary endpoint based on the change from baseline will be assessed using an ANCOVA where the change from baseline will be the dependant variable and including the treatment group and site as fixed effects and baseline value as a covariate. In addition, ANCOVA will also be performed on the change from baseline at week 10 and on the change from Week 8 to Week 10.

All secondary endpoint based on categories will be analysed using a Cochran-Mantel-Haenszel test stratified by site and the p-value from this test will be presented along with frequency and percentage of subjects for each category.

All change and percent change values will be summarized using descriptive statistics, for each treatment group and visit. Proportion of subjects with no, 1-point, 2-point, 3-point, decrease/increase, will be presented at Week 8.

All statistical analyses will be done at each visit and using the ITT (primary analysis) and PP (supportive analysis) population. All the analyses will be done using observed values. Results collected during the early termination visit related to Week 8 and Week 10 will not be included. No sensitivity analysis will be done for missing values.

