	SD	xx.x	xx.x	xx.x
	Median	xx.x	xx.x	xx.x
	Min, Max	xx, xx	xx, xx	xx, xx
	Interquartile	xx, xx	xx, xx	xx, xx
Week 2				
Actual	n	xx	xx	xx
	Mean	xx.x	xx.x	xx.x
	SD	xx.x	xx.x	xx.x
	Median	xx.x	xx.x	xx.x
	Min, Max	xx, xx	xx, xx	xx, xx
	Interquartile	xx, xx	xx, xx	xx, xx
Change from Baseline	n	xx	xx	xx
	Mean	xx.x	xx.x	xx.x
	SD	xx.x	xx.x	xx.x
	Median	xx.x	xx.x	xx.x
	Min, Max	xx, xx	xx, xx	xx, xx
	Interquartile	xx, xx	xx, xx	xx, xx
	LSMEANS ¹	xx.x	xx.x	
	95% CI	(xx.x, xx.x)	(xx.x, xx.x)	
	p-value ¹			
Percent Change from Baseline	n	xx	xx	xx
	Mean	xx.x	xx.x	xx.x
	SD	xx.x	xx.x	xx.x
	Median	xx.x	xx.x	xx.x
	Min, Max	xx, xx	xx, xx	xx, xx
	Interquartile	xx, xx	xx, xx	xx, xx

NOTE: Results at Week 4, Week 8, and Week 10 will also be presented as well as the change from Week 8 to Week 10.

1 LSMEANS and p-value from an ANCOVA on the change from baseline. The model includes Treatment group, Site as fixed effects and the baseline value as the covariate.

Note(s): Baseline is the result measured at Baseline Visit.

Program: t14_2_1_2_1.SAS, Generated on DDMMYYYY HH:MM

Similar tables will be provided for

Table 14.2.1.2.2	Summary of Investigator's Global Assessment - Actual, Change, and Percent Change from Baseline (Per Protocol Population)
Table 14.2.2.1	Summary of Eczema Area and Severity Index - Actual, Change, and Percent Change from Baseline (Intent-to-Treat Population)
Table 14.2.2.2	Summary of Eczema Area and Severity Index - Actual, Change, and Percent Change from Baseline (Per Protocol Population)
Table 14.2.3.1	Summary of Patient-Oriented Eczema Measure - Actual, Change, and Percent Change from Baseline (Intent-to-Treat Population)
Table 14.2.3.2	Summary of Patient-Oriented Eczema Measure - Actual, Change, and Percent Change from Baseline (Per Protocol Population)
Table 14.2.4.1	Summary of Dermatology Quality of Life Index - Actual, Change, and Percent Change from Baseline (Intent-to-Treat Population)
Table 14.2.4.2	Summary of Dermatology Quality of Life Index - Actual, Change, and Percent Change from Baseline (Per Protocol Population)
Table 14.2.5.1	Summary of Summary of SCORing Atopic Dermatitis - Actual, Change, and Percent Change from Baseline (Intent-to-Treat Population)
Table 14.2.5.2	Summary of Summary of SCORing Atopic Dermatitis - Actual, Change, and Percent Change from Baseline (Per Protocol Population)
Table 14.2.6.1	Summary of Visual Analog Scale of Pruritus - Actual, Change, and Percent Change from Baseline (Intent-to-Treat Population)

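### The descriptive percent change from Week 8 to Week 10 divides by a treatment outcome that can be 0 or 1, so it loses cleared subjects and can exaggerate or hide rebound (minor)

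*SAP*

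**What the plan says.** SAP 3.4.2.1 defines the IGA change and percent change from baseline and then adds: "In addition, change and percent change from Week 8 to Week 10 will be calculated". SAP 3.4.2.2 repeats the rule for EASI, BSA, SCORAD, pruritus VAS, POEM, DLQI and TEWL. SAP 7.2 puts the results in the report: "All change and percent change values will be summarized using descriptive statistics, for each treatment group and visit".

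No section says what happens when the Week 8 score is 0. SAP 5.3 rules out filling the gap: "No imputation will be done for all population and all parameters, except for the primary endpoint". SAP section 6 bases the statistics on non-missing values, so a subject with an undefined percentage is simply not counted.

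The entry criteria keep the baseline IGA away from zero: "Moderate to severe atopic dermatitis at baseline as defined by an IGA of minimum 3 at baseline visit". They also require at least 10% BSA at baseline. Nothing similar applies at Week 8, where IGA 0 is part of the treatment goal.

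For inference, SAP 7.2 uses the absolute difference: "In addition, ANCOVA will also be performed on the change from baseline at week 10 and on the change from Week 8 to Week 10". The note to the mock table for change in IGA (SAP 13.1, Table 14.2.1.2.1) also names only the change: "NOTE: Results at Week 4, Week 8, and Week 10 will also be presented as well as the change from Week 8 to Week 10".

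**The concern.** The last dose is taken on the day before the Week 8 visit, so Week 8 to Week 10 is the only off-treatment interval with efficacy scores. A reader will look there for relapse. A percent change is comparable between arms only if its denominator is. Here the denominator is the result of treatment and will differ by arm exactly when the drug works. This has two effects:

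- **Zeros drop out.** A cleared subject who relapses fully does not appear in this summary.
- **Small scores inflate.** One point of worsening counts +100% from IGA 1, +50% from 2, +33% from 3 and +25% from 4.

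At stake is how the descriptive tables portray relapse after stopping. A mean percent worsening that looks larger on DS107G could be read as rebound when the absolute worsening is the same in both arms.

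**Working it through.** **Inputs from the documents.** Planned responder rates are 32% on DS107G and 7% on placebo, with 45 subjects (per arm, as the total of 100 implies), from SAP section 4. Baseline IGA is at least 3, so every subject at IGA 0 or 1 at Week 8 has dropped at least 2 points, and responder means the same as Week 8 IGA 0 or 1.

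**The plan's own figure.** The documents give no figure for this statistic. The nearest is the sample size behind the responder rates. For 32% against 7%, two-sided 0.05 and 80% power, the continuity-corrected formula gives 46 per arm, close to the stated 45. Exact power at 45 per arm is 81.1% for the continuity-corrected chi-square test. With 10% drop-out, 90/0.9 = 100.

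**Assumptions, not in the documents.** A share s of responders is at IGA 0 and the rest at IGA 1. All non-responders are at IGA 3. Everyone worsens by one point, so the true absolute change is +1.0 in both arms.

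With responder rate r:

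- Mean percent change = [100·r(1−s) + 33.3·(1−r)] / [r(1−s) + (1−r)]
- Subjects dropped = 45·r·s

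| s | DS107G mean | Placebo mean | Dropped, DS107G / placebo |
|---|---|---|---|
| 0 | 32 + 22.67 = +54.7% | 7 + 31 = +38.0% | 0 / 0 |
| 0.25 | 46.67/0.92 = +50.7% | 36.25/0.9825 = +36.9% | 3.6 / 0.8 |
| 0.50 | 38.67/0.84 = +46.0% | 34.5/0.965 = +35.8% | 7.2 / 1.6 |
| 1 | 22.67/0.68 = +33.3% | 31/0.93 = +33.3% | 14.4 / 3.2 |

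The apparent rebound comes from denominators of 1. Dropping zeros shrinks it.

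**Non-responders spread 35/45/20% over IGA 2/3/4.** Their average percentage is 0.35×50 + 0.45×33.3 + 0.20×25 = 37.5%.

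- s = 0: DS107G 32 + 0.68×37.5 = +57.5%; placebo 7 + 0.93×37.5 = +41.9%.
- s = 0.5: DS107G 41.5/0.84 = +49.4%; placebo 38.375/0.965 = +39.8%.

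**A milder relapse.** Assume Week 8 IGA 0/1/2/3/4 of 2/5/23/45/25% on placebo and 11/21/30/28/10% on DS107G, which match 7% and 32%. Give every subject a 30% chance of one point of worsening, so the true mean change is +0.30 in both arms.

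- Placebo: 0.3 × (5×100 + 23×50 + 45×33.3 + 25×25)/98 = 0.3 × 3775/98 = +11.6%.
- DS107G: 0.3 × (21×100 + 30×50 + 28×33.3 + 10×25)/89 = 0.3 × 4783/89 = +16.1%.
- Dropped: 45×0.02 = 0.9 and 45×0.11 = 4.95 subjects.

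**The opposite failure.** Let only IGA-0 subjects relapse, from 0 to 2, with s = 0.25. The absolute change is 2×0.32×0.25 = +0.16 on DS107G and 2×0.07×0.25 = +0.035 on placebo. The percent change is 0% in both arms, because every subject who relapsed is missing.

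**Which scores.** A Week 8 score of 0 is possible for IGA, EASI, BSA, VAS, POEM and DLQI. SCORAD is less exposed: IGA 0 means "No evidence of disease with the exception of residual pigment changes and/or xerosis", and dryness is a SCORAD item, so a cleared subject can still score above 0. The documents give no reason to expect a TEWL reading of 0.

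**The case against.** A reader might infer that the off-treatment comparison itself discards the best responders and will show a false rebound. The documents do not support that. The only tested Week 8 to Week 10 comparison is the ANCOVA on absolute change, where a subject who goes from 0 to 3 enters as +3. In the mock table, the inferential results belong to the change block: "LSMEANS and p-value from an ANCOVA on the change from baseline". The percent-change block is descriptive. Week 10 relapse is also shown by the ANCOVA on change from baseline and, for IGA, by the point-change categories with a CMH p-value in Table 14.2.1.3.1. Relapse in cleared subjects is therefore absent from one block of rows, not from the report. No listed primary or secondary endpoint goes beyond Week 8. All of this stands, and it sets the severity.

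A reader might also add the two effects together. They oppose each other, and the net result depends on a split between IGA 0 and 1 that the documents do not give.

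A further defence is that n, median and quartiles appear beside the mean. This helps only in part. In the 30% illustration the median is 0% in both arms. With the 35/45/20 spread, s = 0 and everyone worsening, the medians differ. On DS107G the shares at +25, +33.3, +50 and +100% are 13.6, 30.6, 23.8 and 32.0%, so the median is +50%. On placebo they are 18.6, 41.85, 32.55 and 7.0%, so the median is +33.3%. A lower n also does not tell the reader that the missing subjects include those who cleared.

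**Conclusion.** The point holds for the descriptive percent change from Week 8 to Week 10 only. Its denominator is an outcome of treatment, it is undefined at 0 without a rule, and it is very large near 0. If the drug works, more DS107G than placebo subjects leave the summary. The mean can then overstate rebound or conceal it.

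At the planned responder rates, with one point of worsening for all and non-responders at IGA 3, the gap between arms runs from 16.7 percentage points (54.7 − 38.0) down to none as the share of responders at IGA 0 rises from 0 to 100%. These sizes rest on assumed Week 8 distributions and relapse patterns. The direction of the inflation and the loss of zeros follow from the definition.

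Severity is minor: no tested comparison and no listed primary or secondary endpoint is affected.

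**What to change.** Delete percent change from Week 8 to Week 10 in SAP 3.4.2.1 and for each score in 3.4.2.2, and limit the percent-change summary in 7.2 to change from baseline. Keep the absolute Week 8 to Week 10 change, which is already tested. This also brings the text into line with the mock-table note.

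If a relative measure is wanted, divide the Week 8 to Week 10 change by the baseline score. That denominator is fixed before treatment. Under the entry criteria it cannot be zero for IGA (at least 3) or BSA (at least 10%). It therefore cannot be zero for SCORAD either, where 10% BSA alone contributes 10/5 = 2. A relapse from IGA 0 to 2 with baseline 3 would then count as 2/3 = +66.7% instead of being missing. For scales with no entry minimum, report the number of subjects with a zero baseline by arm.

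The cost is a wording change and one descriptive statistic lost. No new data are needed.
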